## 10.2.6 Protocol Exceptions for Delayed Response ('Pseudo-progression')

Patients in whom the magnitude of increase in tumour size is >20% but <40%, may remain on study for up to 12 weeks after start of protocol therapy if the following criteria are met:

- Lesions <10 mm will not be considered new lesions; new lesions ≥10 mm of longest diameter must be included in the total tumour burden;
- In the judgment of the treating clinician, the patient does not show evidence for rapid disease progression or the patient has shown evidence for clinical benefit;
- There is no decrease in performance status;
- The patient is tolerating the study drug;
- Continued treatment with nivolumab will not delay an imminent intervention required to prevent serious complications (e.g. CNS metastases, which require radiation therapy or surgery).

#### **10.2.7 Confirming Progression**

For patients who remain on study despite increase in tumour size >20%, imaging to include target lesions must occur every cycle if clinically indicated, or if 'pseudo-progression' appears based on inflammatory response, and the same radiographic and clinical criteria must be met in order to remain on study. If tumour size subsequently diminishes to <20% increase from baseline, the patient may be followed according to the standard protocol guidelines which will involve less

frequent imaging. The decision to continue treatment beyond radiographic evidence for disease progression should be discussed with the Study Chair or Co-Chair and documented in the study record.

Unlike RECIST 1.1, iRECIST requires the confirmation of progression. iCPD is confirmed if further increase in tumour burden, compared to the last assessment, is seen as evidenced by one or more of the following:

- Continued increase in tumour burden (from iUPD) where RECIST 1.1 definitions of progression had been met (from nadir) in target, non-target disease or new lesions;
- Progression in target disease worsens with an increase of at least 5 mm in the absolute value of the sum;
- Continued unequivocal progression in non-target disease with an increase in tumour burden;
- Increase in size of previously identified new lesion(s) (an increase of at least 5mm in the absolute value of the sum of those considered to be target new lesions) or additional new lesions;
- RECIST 1.1 criteria are met in lesions types (target or non-target or new lesions) where progression was not previously identified, including the appearance of additional new lesions;
- Clinical stability is considered when deciding whether treatment is continued after iUPD.

If iUPD is not confirmed at the next assessment, then the appropriate response will be assigned (iUPD if the criteria are still met, but no worsening, or iSD, iPR or iCR if those criteria are met compared to baseline). The prior documentation of iUPD does not preclude assigning iCR, iPR, or iSD in subsequent time-point assessments or as best overall response (BOR) providing that iCPD is not documented at the next assessment after iUPD. Tumour disease evaluation will be by objective response rate (ORR = complete response [CR] and partial response [PR]). Patients with response of 'stable disease' (SD), iCR, iPR, or iSD will also be reported as part of the final analysis of clinical benefit, but will not contribute to the primary efficacy outcome measure (Seymour, 2017).

Treatment beyond initial iUPD is permitted in patients who are clinically stable to continue on treatment until the next assessment (≥four [4] weeks later); this next imaging assessment should

be no longer than eight (8) weeks later, to ensure that patients remain fit for salvage therapies All decisions regarding continuation or discontinuation of therapy should be made by the patient, the local PI and either the Study Chair or Co-Chair. An assignment of clinical stability requires that no worsening of performance status has occurred, that no clinically relevant increases in disease-related symptoms such as pain or dyspnoea occur that are thought to be associated with disease progression, and that no requirement for intensified management of disease-related symptoms exists, including increased analgesia, radiotherapy, or other palliative care.

Patients who have iUPD and are not clinically stable should be designated as not clinically stable in the case report form. This designation will allow the best overall response to be calculated and the date of iUPD to be used in estimates of PFS.

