# Exclusion Criteria (Part II only):

to first dose of trial therapy or while on trial are not eligible. The use of physiologic doses of corticosteroids (up to 5mg/m²/day prednisone equivalent) is permitted following discussion with the Study Chair or Co-Chair.

Note: Use of topical, ocular, intra-articular, intra-nasal or inhaled corticosteroids will not render a patient ineligible. A brief course of corticosteroids for prophylaxis (e.g. contrast dye allergy) or for treatment of non-autoimmune conditions (e.g. delayed-type hypersensitivity reaction caused by contact allergen) is permitted if completed at least 7 days prior to initiation of therapy.

- b. **Investigational Drugs:** Patients who are currently receiving another investigational drug are not eligible.
- c. Anti-cancer Agents: Patients who are currently receiving other anticancer agents are not eligible.
- 3. Patients with a History of Autoimmune Disease
- Patients with a history of autoimmune disorder that has required systemic treatment in the previous two (2) years are not eligible.
   Asymptomatic laboratory abnormalities (e.g. ANA, rheumatoid factor, altered thyroid function studies) will not render a patient ineligible in the absence of a diagnosis of an autoimmune disorder. Replacement therapy (e.g. thyroxine, insulin or physiologic corticosteroid replacement therapy) is not considered a form of systemic treatment.
- **4. Infection:** Patients who have an uncontrolled infection are not eligible.
- **5. HIV and/or Hepatitis B/C patients:** Patients with known HIV/AIDS or acute/chronic Hepatitis B or C are excluded.
- **6. Transplant patients:** Patients who have received prior allogeneic Bone Marrow (BM) transplants or prior solid organ transplantation are not eligible.
- **7. Non-Compliance:** Patients who in the opinion of the investigator may not be able to comply with the safety monitoring requirements of the study are not eligible.

	8. Previous anti-PD-1 and/or anti-PD-L1 therapy: Patients who have				
	received prior anti-PD-1 and/or anti-PD-L1 directed therapy (mAb or				
	small molecule) are not eligible.				
	9. Live vaccines: Patients who have received a live vaccine within 30				
	days of start of study treatment are not eligible.				
	Primary efficacy outcome measures:				
	Tumour disease evaluation, includes objective response rate (ORR =				
	complete response [CR] and partial response [PR]) as defined by iRECIST				

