	response criteria for solid tumours (revised for neuroblastoma using the				
	revised INRC), iRANO response criteria for CNS malignancies, RECIL				
	2017 response criteria for lymphomas, revised criteria according to				
	Creutzig, et al. (2012) for acute myeloid leukemia (AML; see Section				
	10.13), and response criteria as specified in Section 10.14 for acute				
Criteria for	lymphoblastic leukemia (ALL).				
Efficacy	Patients with response of 'stable disease' (SD) will also be reported as part				
Evaluation:	of the final analysis of clinical benefit, but will not contribute to the				
	primary efficacy outcome measure.				
	Secondary efficacy outcome measures:				
	PFS is defined as the time from the first dose of the study drug				
	administration to the occurrence of disease progression or death from any cause during the study.				
	OS is defined as time from first dose of study drug to death from any				
	cause.				
	A safety evaluation by the Safety Committee will be performed after				
Criteria for	Patient 1-Cycle 1, Patient 4-Cycle 1, Patient 7-Cycle 1, and Patient 10-				
Safety	Cycle 1. Enrollment will be held after each time point until a safety				
Evaluation:	evaluation of adverse events (AE) and serious adverse events (SAE)				
	confirms it is safe to resume enrollment.				
	confirms it is safe to resume enrollment.				

Toxicities will be described and defined in paediatric patients, focusing on SAEs, using the National Cancer Institute Common Terminology Criteria for Adverse Events (NCI CTCAE), version 4.03. Toxicities (drug-related AEs) of any grade, plus all Grade  $\geq$  3 AEs, all Grade  $\geq$  3 laboratory toxicities and all SAEs as defined in *Section 12* will be collected for this study.

The initial aim for this pilot study was to accrue 20 paediatric patients with biallelic mismatch repair disease (bMMRD) tumours. Following amendment, the study inclusion criteria are expanded to include those with hypermutant tumours (as determined by estimation of TMB by targeted next-generation gene sequencing), as well as patients with CMMRD tumours. Consequently, the total enrollment will be increased to 50 patients.

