#### 10.2.1 Definitions

#### 10.2.1.1 iRECIST Definition

Responses assigned using iRECIST have a prefix of "i", which indicates immune response assigned using iRECIST. For example, "immune" complete response (iCR) or partial response (iPR), and unconfirmed progressive disease (iUPD) or confirmed progressive disease (iCPD) to differentiate them from responses assigned using RECIST 1.1. Similar nomenclature is used for stable disease (iSD). New lesions are assessed and sub-categorized into those that qualify as target lesions (new lesion, target) or non-target lesions (new lesion, non-target).

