## 10.4 Response Criteria for Patients with Solid Tumour and Measurable Disease

## 10.4.1 Time Point and Best Overall Response

The time point response is calculated using the response assigned for each category of lesion (as for RECIST 1.1), but takes into account the last time point response. The algorithm for patients with no previous iUPD is identical to RECIST 1.1 (Eisenhaur, 2009). For patients with iUPD at the last time point response, the next time point response is dependent on the status of all lesions, including target, non-target, new lesion target, and new lesion non-target; on whether any increase in size has occurred (either a further increase in size or a sufficient increase to assign a new iUPD if the criteria were not previously met); or the appearance of additional new lesions.

For iRECIST, the best overall response (iBOR) is the best time point response recorded from the start of the study treatment until the end of treatment, considering any requirement for confirmation. iUPD will not override a subsequent best overall response of iSD, iPR, or iCR, meaning that iPR or iSD can be assigned (time point response or iBOR) even if new lesions have not regressed, or if unequivocal progression (non-target lesions) remains unchanged, providing that the criteria for iCPD are not met. The duration of iCR and iPR is from the time point when the criteria for iCR or iPR are first met, whereas the duration of iSD is still calculated from baseline.

Assessments that are not done or are not evaluable should be disregarded. For example, an iUPD followed by an assessment that was not done or not evaluable, and then another unconfirmed progressive disease, would be indicative of iCPD.

Assessments done after protocol therapyis discontinued can be considered in identification of iBOR. All imaging done during the follow-up period should continue to be recorded on the case report form ad used to assess response until subsequent therapies are initiated, as the protocol and informed consent document permit.

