#### Cytogenetic complete remission (CRc):

- The patient must also have attained and be assigned morphologic response of CR or CRp or CRi as defined above.
- Must have a revision to a normal karyotype with a minimum analysis of 20 metaphases.

**Partial Response (PR):** A decrease of at least 50% blasts percentage (to M2: 5% to 25%) in the BM aspirate. BM must have adequate cellularity (e.g., > 15%) to determine response. PR status will not be included in calculation of response to the regimen.

A repeat BM aspiration after several weeks may be required to distinguish between a PR and increased blasts caused by BM regeneration. A value of < 5% blasts may also be considered a PR if Auer rods are present.

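### Section 10.2.7 keeps iCR and iPR out of the primary outcome, while the synopsis counts iRECIST CR and PR and excludes only SD

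*Protocol*

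**What the plan says.** The synopsis (Criteria for Efficacy Evaluation) gives the primary measure as ORR, made up of "complete response [CR] and partial response [PR]) as defined by iRECIST" for solid tumours, with other named criteria for other diagnoses. It sets one category aside: "Patients with response of 'stable disease' (SD) will also be reported as part" of the clinical-benefit analysis, without counting towards the primary measure.

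Section 10.2.1.1 sets the labelling rule: "Responses assigned using iRECIST have a prefix of" the letter i. A CR or PR assigned under iRECIST is therefore written iCR or iPR.

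Section 10.2.7 first restates the endpoint: "Tumour disease evaluation will be by objective response rate (ORR = complete response [CR] and partial response [PR"). The next sentence follows the synopsis sentence on SD but lengthens its list of what stays out of that measure: "iCR, iPR, or iSD will also be reported as part of the final analysis of clinical benefit, but will not contribute to the primary".

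Section 10.4.1, on best overall response, says "iUPD will not override a subsequent best overall response of iSD, iPR, or iCR". Section 10.4.2 defines CR and PR without the prefix. Section 11 applies the Simon rules to objective responses (CR+PR) and does not say whether iCR and iPR are included.

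**The concern.** The numerator of the primary endpoint is fixed in two ways that cannot both be followed. Under the synopsis, a solid-tumour patient with an iRECIST partial response is a responder. Under Section 10.2.7, at least some such patients are not.

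The responder count drives every cohort decision: close at 1 or fewer of 10, and reject the null at 5 or more of 20 (Cohort A) or 6 or more of 30 (Cohort B). With thresholds this small, one patient can matter. If Cohort A has 5 responders in 20 and one of them responded after iUPD, the synopsis gives 5/20 and the null is rejected. Section 10.2.7 gives 4/20 and it is not.

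An SAP cannot settle this alone, because either choice would contradict one section of the protocol.

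**Working it through.** **Reading the passages together**

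| Place | Counts towards ORR | Kept out |
|---|---|---|
| Synopsis | CR, PR by iRECIST | SD |
| 10.2.7, first sentence on ORR | CR, PR (no prefix) | – |
| 10.2.7, next sentence | – | SD, iCR, iPR, iSD |
| 11 | CR+PR, prefix not addressed | – |

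Two readings of Section 10.2.7 are open:
- *Narrow.* Unprefixed CR and PR (Section 10.4.2) count, and only iCR or iPR reached after iUPD is dropped.
- *Literal.* With the labelling rule of Section 10.2.1.1, every iRECIST response is an iCR or iPR, so all are dropped.

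The synopsis makes neither exception.

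**Who is affected.** Only patients assessed by iRECIST. CNS tumours (iRANO), neuroblastoma (revised INRC), lymphoma (RECIL 2017), AML and ALL have their own criteria.

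**Effect on the Simon rules**

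Inputs from Section 11:
- Both cohorts: 10 patients in stage 1; close at 1 or fewer responses.
- Cohort A: total n = 20, reject at r = 5, alternative p1 = 0.35, stated power 85%.
- Cohort B: total n = 30, reject at r = 6, alternative p1 = 0.30, stated power 80%.

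Formulas, with p the counted response rate:
- Power = Σ over x = 2 to 10 of P(Bin(10, p) = x) × P(Bin(n − 10, p) ≥ r − x).
- Probability of closing at stage 1 = (1 − p)^10 + 10p(1 − p)^9.

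The plan's own figures first, at p = p1: power is 0.843 in Cohort A and 0.815 in Cohort B. Both agree with the stated values to within 2 percentage points. Closing at stage 1 in Cohort A is 0.65^10 + 10 × 0.35 × 0.65^9 = 0.0135 + 0.0725 = 0.086.

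Next, let s be the share of true responses not counted, so that p = p1 × (1 − s). The documents do not give s, so a range is shown:

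| s | p, A | Power, A | Closing, A | p, B | Power, B | Closing, B |
|---|---|---|---|---|---|---|
| 0% | 0.350 | 84% | 9% | 0.300 | 81% | 15% |
| 10% | 0.315 | 76% | 13% | 0.270 | 73% | 20% |
| 30% | 0.245 | 52% | 26% | 0.210 | 50% | 35% |
| 50% | 0.175 | 24% | 46% | 0.150 | 22% | 54% |

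Under the narrow reading, s is the share of all responders who were assessed by iRECIST and responded after iUPD. Under the literal reading, it is the share of all responders who were assessed by iRECIST.

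**The case against.** The best defence is that Section 10.2.7 must be read whole. The sentence just before the disputed one keeps ORR as CR plus PR. Section 10.4.2 defines those categories without the prefix, and Section 11 counts them. Section 10.4.1 makes the algorithm identical to RECIST 1.1 when there has been no previous iUPD, and Section 10.2.5 has patients with progressive disease evaluated by iRECIST as well. The paragraph that holds the disputed sentence opens with iUPD that is not confirmed. In context, the sentence sets aside only responses after iUPD.

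Most of this stands. A reader might infer from Sections 10.2.1.1 and 10.2.7 that no solid-tumour patient can ever be a responder, so that responses are all counted or none. The words allow that, but it would empty the ORR sentence beside it, and the narrow reading is more plausible.

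The defence does not remove the conflict. The protocol nowhere states the narrow reading, and the synopsis has no exception for responses after iUPD. Section 10.2 explains that iRECIST was adapted because apparent growth may not be true progression. The same paragraph of Section 10.2.7 lets iCR or iPR be the best overall response after iUPD if confirmed progression (iCPD) is not documented at the next assessment. Section 10.4.1 agrees, although it governs best overall response and does not itself say that such a response enters the primary ORR.

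A reader might also see a second conflict in Section 10.13, which says of AML that "PR status will not be included in calculation of response to the regimen". The documents do not support that. The synopsis defines ORR by disease-specific criteria and sends AML to Section 10.13, so this is a disease-specific rule reached by the synopsis's own cross-reference.

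**Conclusion.** The concern holds in limited form. One sentence of Section 10.2.7 contradicts the synopsis on whether iCR and iPR count towards the primary endpoint, and Section 11 does not resolve it. The conflict is confined to patients assessed by iRECIST and most plausibly to their responses after iUPD. Either reading of the sentence can only lower the responder count relative to the synopsis.

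The contradiction is textual and does not depend on the power figures. Those show how sensitive the design is: at an assumed loss of 10% of responses, power falls by about 8 percentage points in each cohort, and at 50% it falls to 24% (A) and 22% (B). No loss share has a source in the documents, so none of these is an estimate for this trial. A cohort's conclusion changes only if the uncounted responses move the total across a boundary.

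**What to change.** In Section 10.2.7, strike iCR and iPR from the sentence so that only SD and iSD stay outside the primary outcome. In Section 11, state that for patients assessed by iRECIST, ORR counts a best overall response of iCR or iPR, including one reached after iUPD that was not followed by iCPD. This agrees with the synopsis and with best overall response in Section 10.4.1.

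If the sponsor instead intends RECIST 1.1 CR and PR as the primary measure, the synopsis must be changed to say so and Section 11 worded to match. Section 10.13 needs no change on this account.

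The cost is a short wording amendment, with no new data and no change to sample size. Because the trial is open-label, the choice should be made before response counts are used for a cohort decision, so that it cannot follow the results.

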## **10.2** Response Criteria for Patients with Solid Tumours

See the table in *Section 8* and *8.2* for the schedule of tumour evaluations. In addition to the scheduled scans, a confirmatory scan should be obtained 28 days following initial documentation of objective response.

Response and progression will be evaluated in this study using the modified Response Evaluation Criteria in Solid Tumours (RECIST 1.1) for immune-based therapeutics guidelines deemed iRECIST (Seymour, 2017). Immunotherapeutics may result in infiltration of immune cells leading to transient increase in the size in malignant lesions, or undetectable lesions becoming detectable ('pseudo-progression'). The criteria are identical to those of RECIST 1.1 (Eisenhaur, 2009) in many respects but have been adapted to account for instances where an increase in tumour burden, or the appearance of new lesions, does not reflect true tumour progression.

RECIST 1.1 will continue to be used to define whether tumour lesions, including lymph nodes, are measurable or non-measurable, as well as for the management of bone lesions, cystic lesions, and lesions with previous local treatment and the method of measurement (Eisenhaur, 2009). The principles used to establish objective tumour response are largely unchanged from RECIST 1.1. The major change from RECIST 1.1 is the concept of resetting the bar if progression is followed at the next assessment by tumour shrinkage (Seymour, 2017).

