## 10.4.3 Evaluation of Non-Target Lesions

**Complete Response (CR):** Disappearance of all non-target lesions and normalization of tumour marker level. All lymph nodes must be non-pathological in size (<10 mm short axis).

**Note:** If tumour markers are initially above the upper normal limit, they must normalize for a patient to be considered in complete clinical response.

**Non-CR/Non-PD:** Persistence of one or more non-target lesion(s) and/or maintenance of tumour marker level above the normal limits.

**Progressive Disease (PD):** Appearance of one or more new lesions and/or unequivocal progression of existing non-target lesions. Unequivocal progression should not normally trump target lesion status. It must be representative of overall disease status change, not a single lesion increase.

**Best Overall Response (iBOR):** Each patient will be classified according to his "best response" for the purposes of analysis of treatment effect. Best response is determined as outlined in *Section* 10.4.1 and 11 from a sequence of overall response assessments.

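### Section 10.2.7 keeps iCR and iPR out of the primary efficacy measure, while the synopsis defines solid-tumour ORR by iRECIST and leaves out only stable disease

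*Protocol*

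**What the plan says.** The synopsis (Criteria for Efficacy Evaluation) gives the primary measure as ORR, made up of "complete response [CR] and partial response [PR]) as defined by iRECIST" for solid tumours, with other criteria for other diseases. It then names one category that is reported but does not count: "Patients with response of 'stable disease' (SD) will also be reported as part" of the clinical-benefit analysis.

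Section 10.2.7 defines ORR as CR plus PR and then repeats the synopsis sentence with a longer list. After stable disease it continues: "iCR, iPR, or iSD will also be reported as part of the final analysis of clinical benefit, but will not contribute to the primary" efficacy measure.

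Three other places bear on what the labels mean:

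- Section 10.2.1.1: "Responses assigned using iRECIST have a prefix of" the letter i.
- Section 10.4.1: "iUPD will not override a subsequent best overall response of iSD, iPR, or iCR". Section 10.2.7 says much the same two sentences before the disputed one.
- Section 10.4.3 classifies each patient by best response "for the purposes of analysis of treatment effect".

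Section 11 bases both cohort decisions on a count of objective responses, written as CR+PR without further definition.

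**The concern.** The synopsis scores solid tumours by iRECIST, and iRECIST responses carry the prefix i. The responses it counts therefore include iCR and iPR, which 10.2.7 names as not counting. Two analysts working from the same data, one from each text, could report different numbers of responders.

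That number decides each cohort. A cohort closes at 1 or fewer responses in the first 10 patients. The null is rejected at 5 or more of 20 in Cohort A and at 6 or more of 30 in Cohort B. Near a boundary one patient is enough. If Cohort B had 6 responders and one of them had responded after an iUPD, the synopsis would give 6 and rejection. Section 10.2.7 would give 6 − 1 = 5 and no rejection.

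**Working it through.** **Text, side by side**

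| Place | Counts towards ORR (solid tumours) | Does not count |
|---|---|---|
| Synopsis | CR and PR by iRECIST | SD |
| 10.2.7 | CR and PR | SD, iCR, iPR, iSD |
| Section 11 | CR+PR | not stated |

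The sentence in 10.2.7 can be read literally in two ways.

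1. *Every iRECIST-scored response is left out.* Solid-tumour ORR would then be zero by construction, and the ORR definition in the sentence just before would be empty.
2. *Only responses after an iUPD are left out*, with unprefixed CR and PR kept for patients without one. This is the more tenable reading, because Sections 10.4.2, 10.4.3 and 10.5 and Tables 5 and 7 all define responses without the prefix.

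The second reading still contradicts the synopsis. The synopsis uses iRECIST, under which a response after an unconfirmed progression is a response, and it excludes only SD.

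**Reproducing the plan's power**

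Inputs from Section 11:

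- Both cohorts: 10 patients in stage 1, continue with 2 or more responses.
- Cohort A: 10 more patients, reject at r = 5 or more in total, true rate 0.35.
- Cohort B: 20 more patients, reject at r = 6 or more in total, true rate 0.30.

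Power = sum over x1 = 2 to 10 of P(X1 = x1 | 10, p) × P(X2 ≥ r − x1 | n2, p), where n2 is the stage 2 number.

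- Cohort A at p = 0.35: 0.843 (protocol: 85%).
- Cohort B at p = 0.30: 0.815 (protocol: 80%).

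**Illustration of an undercount**

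Let f be the share of true responders excluded under 10.2.7. The documents give no value, so f is an assumption. The counted response rate becomes p × (1 − f).

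| f | Cohort A rate | Cohort A power | Cohort B rate | Cohort B power |
|---|---|---|---|---|
| 0 | 0.35 | 0.843 | 0.30 | 0.815 |
| 5% | 0.35 × 0.95 = 0.3325 | 0.805 | 0.30 × 0.95 = 0.285 | 0.777 |
| 10% | 0.35 × 0.90 = 0.315 | 0.760 | 0.30 × 0.90 = 0.27 | 0.734 |

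The loss is about 4 points at f = 5% and about 8 points at f = 10%. Under the second reading, f is the share of responses scored by iRECIST multiplied by the share of those that follow an iUPD. For example, 50% × 10% = 5%.

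**The case against.** The best defence is that 10.2.7 may reflect a deliberate, conservative choice. Section 10.2.1.1 says the prefix separates these responses from those assigned by RECIST 1.1. Section 10.2.5 says patients with progression will also be evaluated by iRECIST. Section 10.4.1 says that without a prior iUPD the algorithm is the same as RECIST 1.1. On that view, post-iUPD responses are recorded and reported, but kept out of the primary count. This makes the second reading intelligible. It does not reconcile it with the synopsis, and no section makes RECIST 1.1 response the primary measure.

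Four stronger conclusions are tempting, and the documents do not support them.

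- *All solid-tumour responses are excluded.* This depends on labels that the protocol's own response definitions do not use. A site following 10.4.2 would record PR, which 10.2.7 does not exclude.
- *Sections 10.4.1 and 10.4.3 flatly contradict 10.2.7.* They govern how best response is assigned and used, and neither mentions ORR. A response can be assignable as best response and still be left out of the primary measure. They are in tension with 10.2.7; the firm conflict is with the synopsis.
- *Power falls heavily.* CNS tumours, lymphoma and leukaemia have their own criteria, and neuroblastoma follows modified INRC. Section 1.1 puts brain tumours at 36–48% in CMMRD and leukaemia or lymphoma at about one third of patients, although enrolment is now wider than CMMRD. Nothing supports a large f under the tenable reading.
- *Only confirmed iCR and iPR should count.* Section 10.2 says "a confirmatory scan should be obtained 28 days following initial documentation of objective response", but the synopsis sets no confirmation condition for ORR. Adding one would change the endpoint.

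**Conclusion.** The point holds as an internal contradiction on which solid-tumour responses enter the primary endpoint. The synopsis makes a drafting slip in 10.2.7 the likely explanation. Even so, 10.2.7 is the body text for solid tumours, and Section 11 does not say which version governs.

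The harm arises only if 10.2.7 is followed as written, and only for tumours scored by iRECIST. It runs in one direction: fewer responses counted, so an active cohort is more likely to close early or miss its threshold. The size is unknown from the documents. The 4 and 8 point losses of power rest on assumed shares of 5% and 10% and on the response rates in Section 11; they are not estimates.

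**What to change.** In Section 10.2.7, delete iCR and iPR from the sentence, so that only SD and iSD are reported under clinical benefit and kept out of the primary measure. Then add: *For solid tumours, iCR and iPR, including after an iUPD not followed by iCPD, count as CR and PR for ORR.* This brings the section into line with the synopsis. Add no new confirmation condition.

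The cost is the wording of one short passage in an amendment. No scans, patients or changes to the decision rules are needed.
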